6.5.1 Study Time and Events Table

Study Procedures			
	Pre- Endoscopy Procedure	Day of Proce- dure	Follow- up
Study Interval			
Informed consent	X		
Demographics	X		
Medical history	X		
Surgical history	X		
Medication History	X		X
INR	X		
Platelet Count	X		
Height (in)	X		
Weight (lb)	X		
BMI	X		
Urine Pregnancy test, when applicable	X		
Randomization regarding needle type		X	
EUS-LB		X	
Adverse events ^a	X-----X		
^a From the signing of the informed consent form to 1 week post-EUS-LB INR = international normalized ratio, BMI = Body Mass Index (lb/in ²), EUS-LB = Endoscopic Ultrasound Guided Liver Biopsy			

All activities are standard of care, except for the selection of needle type.

Follow-up will be conducted via phone call.

6.6 Primary Endpoints

1. Proportion of cases for which a histologic diagnosis could be made based upon the amount of tissue obtained with the needle.
2. Number of portal tracts (PT) in the specimen [34-36]

Date Last Modified: 10/2/2017

IRB # 2017-0391

CONFIDENTIAL AND PROPRIETARY

3. Aggregate specimen length (ASL), length of the longest piece (LLP), and degree of fragmentation

6.7 Secondary Endpoints

1. Presence of a visible core specimen
2. Presence of visible clots in specimen
3. Adverse events (AE) and serious adverse events (SAE)

6.8 Statistics

A representative from the Biostatistics & Research Data Core will be doing the statistical analysis.

6.8.1 Statistical Analysis Plan

Assuming the 19-g FNB needle has a success percentage of 98% (ie, ≥ 5 portal triads), and margin over FNA needle of 5% (98% vs. 93%), the study needs to evaluate 32 patients to achieve 80% power for a 1-sided non-inferiority test. This also assumes each patient provides 2 specimens. If the margin is increased to 10% (98% vs. 88%), then the study needs to evaluate 18 patients to achieve 80% power.

Descriptive statistics will be utilized to represent continuous and categorical variables, with results expressed as medians with ranges. Multiple comparisons between the aggregate tissue length and CPT yield from bilobar, left lobe only, and right lobe only biopsies will be carried out using the Mann-Whitney-Wilcoxon test. A P-value of <0.05 will be considered statistically significant.

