4 HYPOTHESIS AND SPECIFIC AIMS

4.1 Hypothesis

We predict that the 19-g FNA needle and 19-g FNB needle will have similar ability to obtain adequate EUS-LB specimens

4.2 Specific Aim 1

To determine the adequacy of EUS-LB using a 19-g FNB needle as compared with 19-g FNA needle.

4.3 Specific Aim 2

To determine if the 19-g FNB needle will demonstrate less blood artifact during the time of EUS-LB as compared with 19-g FNA needle.

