6 STUDY DESIGN

6.1 Description

This is a prospective randomized trial comparing the biopsy specimen adequacy (SA) of 19-g FNA versus 19-g FNB needle for EUS-LB.

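### The needle comparison that patients are randomised for has no specified endpoint or analysis, and the 80% power stated for it at the 5-point margin is not reached with 32 patients.

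*Combined protocol and SAP*

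**What the plan says.** **Sizing (6.8.1, first paragraph).** The FNB needle is assumed to have a "success percentage of 98% (ie, ≥ 5 portal triads"). With a 5% margin over FNA (98% and 93%), 32 patients are said "to achieve 80% power for a 1-sided non-inferiority test". The next sentence reads "This also assumes each patient provides 2 specimens". A second scenario follows, "If the margin is increased to 10% (98% vs. 88"%), for which 18 patients are given.

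**Analysis (6.8.1, second paragraph).** After descriptive statistics, one inferential analysis is described: "Multiple comparisons between the aggregate tissue length and CPT yield from bilobar, left lobe only, and right lobe only biopsies", by the Mann-Whitney-Wilcoxon test. A general significance threshold of P<0.05 closes the section.

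**Endpoints (section 3 and 6.6).** Three numbered primary items cover five measures: whether a histologic diagnosis was possible, the portal tract count, total specimen length, longest piece, and fragmentation. None is ranked first and none carries a cut-off of 5. The secondary list (section 3 and 6.7) has no such cut-off either.

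**Question.** Section 6.1 describes a "prospective randomized trial comparing the biopsy specimen adequacy (SA) of 19-g FNA versus 19-g FNB needle". The hypothesis in 4.1 is "similar ability to obtain adequate EUS-LB specimens", and Specific Aim 1 (4.2) is "To determine the adequacy of EUS-LB using a 19-g FNB needle as compared with 19-g FNA needle". Adequacy is not defined in any of these. Section 6.8.2 restates the needle question and the 32 cases, but adds no endpoint or test.

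**The concern.** Needle type is what is randomised, and every statement of purpose is about needles. A statistician who follows the analysis paragraph literally would produce p-values by lobe and would have no instruction for the needle comparison. The success definition that drove the sample size would have to be carried over from the power sentence, and the test method and unit of analysis chosen, possibly after the data are seen.

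A related gap is terminology. The count is called portal triads, portal tracts and CPT. The abbreviation list also has partial portal tracts, and nothing says whether these count towards 5.

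The stated power matters as well. If 32 patients cannot support a 5-point non-inferiority claim, a failure to show non-inferiority would say little about the needle.

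**Working it through.** **Inputs.** From 6.8.1: FNB rate 98%; FNA rate 93% (5-point margin) or 88% (10-point margin); 80% power; one-sided test; 32 or 18 patients; 2 specimens per patient. From 6.2.1: about 32 subjects in all. Assumed, because the plan does not say: 1:1 allocation, one needle per patient, no dropout, and one-sided alpha 0.05 or 0.025. This gives 16 patients × 2 = 32 specimens per needle, so total patients equal specimens per needle.

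**1. The plan's own figure.** Margin over FNA of 5% (98% and 93%) can be read in two ways: equal true rates of 98% with a 5-point margin, or a true 98% against 93% with a 5-point margin. The usual normal-approximation size per needle is

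n = (z_alpha + z_beta)² × [pB(1−pB) + pA(1−pA)] / (pB − pA + m)²,

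with (1.645 + 0.842)² = 6.183 at one-sided 0.05 (B = FNB, A = FNA).

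- m = 0.05, 98% and 98%: 6.183 × 0.0392 / 0.0025 = 96.9, so 97 patients.
- m = 0.05, 98% and 93%: 6.183 × 0.0847 / 0.01 = 52.4, so 53 patients.
- m = 0.10, 98% and 98%: 6.183 × 0.0392 / 0.01 = 24.2, so 25 patients.
- m = 0.10, 98% and 88%: 6.183 × 0.1252 / 0.04 = 19.4, so 20 patients.

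The plan gives 32 and 18. None of the variants tried gave both.

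**2. Power with 32 specimens per needle, normal approximation, 5 points.** Power = Φ[(pB − pA + m)/SE − z_alpha].

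- 98% and 98%: SE = √(0.0392/32) = 0.0350; 0.05/0.0350 − 1.645 = −0.216; power 41% (30% at 0.025).
- 98% and 93%: SE = √(0.0847/32) = 0.0514; 0.10/0.0514 − 1.645 = 0.299; power 62% (49% at 0.025).

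**3. Exact power, 5 points.** The normal approximation is unreliable near 100%, so power was also found by summing binomial probabilities over all outcomes. The test was the score test, z = (observed difference + m)/SE, with SE from the rates fitted under a true difference of −m. Each cell gives one-sided 0.05 / 0.025.

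| Units per needle | 98% and 98% | 98% and 93% |
|---|---|---|
| 32 (specimens independent) | 26% / 7% | 61% / 41% |
| 16 (a patient's two specimens always agree) | 3% / 0.3% | 23% / 7% |

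**4. No failures in either arm.** The fitted rates are 1−m and 1, so z = m/√(m(1−m)/n). At m = 0.05:

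- by specimen, n = 32: 0.05/√(0.0475/32) = 1.298, p = 0.097;
- by patient, n = 16: 0.05/√(0.0475/16) = 0.918, p = 0.179.

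Neither shows non-inferiority at 0.05.

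**5. The 10-point margin, 32 independent specimens per needle, one-sided 0.05.** Exact score-test power is 57% at 98% and 98%, 79.6% at 98% and 93%, 83.0% at 98% and 92%, and 93% at 98% and 88%. So about 80% is reached once FNB is truly some 5 to 6 points better.

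**The case against.** Several stronger readings are tempting, and the documents do not support them.

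- *No needle test is planned.* A one-sided non-inferiority test of the needles is named under the statistical analysis plan heading. What is missing is its specification.
- *The planned test certainly compares lobes.* Both lobes are sampled in each patient (6.5), so left and right are paired, whereas Mann-Whitney-Wilcoxon is for independent groups. The sentence may mean needle comparisons within bilobar, left and right samples. It does not say so.
- *No alpha is given.* P<0.05 closes the section. It is not tied to the one-sided test, but one-sided 0.05 is a reasonable reading, and the shortfall is present there.
- *The margin is open.* The plan ties 32 patients to 5 points, and 6.2.1 and 6.8.2 adopt 32. The 10-point line reads as an alternative scenario.
- *At 10 points, 80% power needs a true 10-point advantage.* At one-sided 0.05 it does not (step 5).

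Two further defences have some force. Portal tract count is a listed primary item and the wording leans towards specimens as the unit, so the sizing variable is not foreign to the endpoints. But the cut-off, the lead status and the clustering of two specimens per patient are still unstated.

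The zero-failure result also depends on method. An unadjusted Wald limit would be 0 and would pass, a known defect when there are no failures. An Agresti-Caffo limit by specimen (−0.067 at one-sided 0.05) would fail at 5 points. The power shortfall is less sensitive: with 32 independent specimens per needle, exact Wald power at 0.05 is 53% (98% and 98%) and 67% (98% and 93%), still below 80%.

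Finally, if 32 meant patients per needle, 98% and 93% would need about 33 to 34 per needle, close to the stated figure. But the matching 10-point figure would be 13, not 18, and 6.2.1 gives 32 as the total.

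**Conclusion.** The point holds. The plan names a needle non-inferiority test in its sizing sentence but does not specify it. The success definition behind it is in no endpoint list, no primary measure leads, and the only test in the analysis paragraph does not mention the needles.

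At the 5-point margin attached to the 32 patients, the stated 80% is not delivered. Exact score-test power at one-sided 0.05 is 26% or 61%, depending on how the margin sentence is read, and it falls to 3% or 23% if a patient's two specimens always agree. These figures rest on 1:1 allocation, one needle per patient, no dropout and the score test. The structural gap rests on none of them.

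The power result does not mean that non-inferiority at 5 points is impossible. By the score test it needs FNB to do better than FNA in the sample; two perfect arms are not enough.

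**What to change.** 1. **Lead endpoint (6.6 and section 3).** Name one. The default is the one used for sizing, at least 5 portal tracts, with one term for the count throughout and a statement of whether partial tracts count. If the sponsor prefers histologic diagnosis as the lead, the power statement must be redone for it.
2. **Needle analysis (6.8.1).** Add the FNB minus FNA difference in the proportion meeting the lead endpoint, with a score-based one-sided confidence limit compared with one margin fixed and justified before data are seen. State the one-sided alpha, and either use one result per patient or analyse specimens with an allowance for clustering.
3. **Other measures.** Report the remaining primary measures as supportive needle differences with 95% confidence intervals. Label any lobe comparisons exploratory.
4. **Power (6.8.1 and 6.8.2).** Replace the 80% with the power that 32 patients give for that test. If 5 points is kept, say that the score test could not show non-inferiority even with no failures in either arm.

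The cost is wording, with no new visit, procedure or patient. A rule for annotating slides is needed only if complete and partial tracts are not already recorded separately. The downside is that the other measures lose equal primary status and the stated power becomes less favourable.

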6.8.2 Statistical Power and Sample Size Considerations

The purpose of this study to determine if the 19-g FNB EUS needle provides liver cores equal or superior to 19-g FNA needle for histologic interpretation. A few preliminary cases utilizing the 19g core needle have been found to provide adequate cores. It is felt that 32 cases collected prospectively should be adequate to learn how the 19g FNB needle compares to the 19g FNA needle in different patients with different liver conditions.

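### The non-inferiority margin in 6.8.1 is written as FNB's lead over FNA, so no limit is set on how much worse FNB may be, which is the question in 6.8.2

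*Combined protocol and SAP*

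**What the plan says.** Section 6.8.1 begins "Assuming the 19-g FNB needle has a success percentage of 98" per cent, where success means at least 5 portal triads. It then sets a "margin over FNA needle of 5% (98% vs. 93" per cent and concludes that "the study needs to evaluate 32 patients" to reach "80% power for a 1-sided non-inferiority test", with two specimens from each patient. A second scenario follows: "If the margin is increased to 10% (98% vs. 88" per cent, for which 18 patients are said to be enough.

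The section gives no null or alternative hypothesis, reference needle or rejection rule for this test. Its only significance threshold is general: "A P-value of <0.05 will be considered statistically significant". The analysis paragraph that follows describes summaries and Mann-Whitney-Wilcoxon comparisons, not a non-inferiority test.

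Section 6.8.2 states the purpose: to "determine if the 19-g FNB EUS needle provides liver cores equal or superior to 19-g FNA needle for histologic interpretation". The Abstract calls FNA the conventional needle. Section 4.1 is symmetric and predicts that the "19-g FNA needle and 19-g FNB needle will have similar ability to obtain adequate EUS-LB specimens".

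**The concern.** A non-inferiority margin is the largest shortfall of the needle under test, relative to the reference, that would still be accepted. Section 6.8.2 and the Abstract make FNB the needle under test and FNA the reference, so the margin should lie below FNA. Section 6.8.1 measures the 5 (or 10) points in the other direction, as the amount by which FNB exceeds FNA.

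The direction can decide the conclusion. A one-sided test that protects against a poor FNA needle answers a different question from one that protects against a poor FNB needle, and the two can give opposite results on the same data. Section 6.8 leaves the analysis to a statistics core, which would have to choose the direction itself. The 80% power is also tied to a quantity that is not a margin for the trial's question.

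**Working it through.** **Inputs.** From 6.8.1: FNB 98%; 93% or 88% as the second figure; 5 or 10 points; 80% power; one-sided; 32 or 18 patients; 2 specimens per patient. Assumptions, because the plan does not state them: 1:1 allocation with one needle per patient, so 32 × 2 / 2 = 32 specimens per needle (18 in the second scenario); independent specimens within a patient; one-sided alpha of 0.05 or 0.025.

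**Step 1: the plan's own figure.** For test needle T, reference R and margin M, the usual unpooled formula for specimens per needle is

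n = (z₁₋α + z₀.₈)² [p_T(1−p_T) + p_R(1−p_R)] / (p_T − p_R + M)²

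where (z₁₋α + z₀.₈)² is 6.18 at alpha 0.05 and 7.85 at 0.025.

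- Both needles 98%, M = 5 points: 6.18 × 0.0392 / 0.0025 gives 97; at alpha 0.025, 124.
- FNB 98% as T, FNA 93% as R, M = 5 points: 6.18 × 0.0847 / 0.01 gives 53; at alpha 0.025, 67.
- FNB 98% as T, FNA 88% as R, M = 10 points: 6.18 × 0.1252 / 0.04 gives 20; at alpha 0.025, 25.
- FNA as T at 93%, FNB as R at 98%, M = 5 points: the denominator is zero, so no sample size exists.

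The plan implies 32 and 18 per needle. No variant tried gives both, including score, continuity-corrected, one-sample, arcsine, logit and log-ratio forms at alpha 0.025, 0.05 and 0.10. There are two near matches to 32, both at alpha 0.025. A one-sample test of 98% against 93% needs 62 specimens (31 patients), but only 16 specimens (8 patients) for 10 points. The 67 specimens above are 34 patients per arm, but the 10-point case is then 13 per arm. The arithmetic therefore does not show which reading was meant.

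**Step 2: the two readings.**

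| Reading of 98% and 93% | What the test would show | Limit on an FNB shortfall |
|---|---|---|
| A: 93% is the lowest acceptable FNA rate | FNA non-inferior to FNB | None |
| B: both are expected rates | Direction may be right, but the 5 points are an assumed FNB advantage | None stated |

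**Step 3: consequence of direction.** The score statistic is

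Z = (p̂_T − p̂_R + M) / √{[p̃_T(1−p̃_T) + p̃_R(1−p̃_R)] / n}

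where p̃ are the maximum-likelihood rates under p̃_T = p̃_R − M. The test passes if Z > z₁₋α. The pass probability is the sum of binomial probabilities over all passing pairs of counts, with n = 32 per needle and M = 5 points.

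| True FNB / FNA | Reading A (FNA as test), alpha 0.05 / 0.025 | Direction 6.8.2 needs (FNB as test), alpha 0.05 / 0.025 |
|---|---|---|
| 88% / 98% | 81% / 68% | 1.0% / 0.3% |
| 98% / 93% | 5.3% / 1.4% | 61% / 41% |
| 98% / 98% | 26% / 7% | 26% / 7% |

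Hand check on the last row: if all 32 specimens succeed with both needles, then p̃_R = 1 and p̃_T = 0.95. The standard error is √(0.95 × 0.05 / 32) = 0.0385 and Z = 0.05 / 0.0385 = 1.30, below 1.645. Even a perfect tie does not pass at alpha 0.05.

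**Step 4: sensitivity to method.** Exact enumeration of the unpooled Wald test gives 82% / 73% for the 81% / 68% cell and about 2% for the needed direction in that row. At alpha 0.05 its power in the needed direction is 67% at 98% against 93%, and 53% with both at 98%. It exceeds its nominal level, however: about 10% at a true 5-point deficit. Neither method reaches 80%.

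**The case against.** A reader might infer that the plan's test is simply backwards, and that the trial as written will pass a clearly worse FNB needle. The documents do not support that as fact. Section 6.8.1 contains a sample-size sentence, not a defined test. Its words can equally mean expected rates of 98% and 93%, in which case the direction is not wrong and the defect is a missing margin. Section 6.8.2, Aim 1 and the Abstract all point to FNB as the needle under test, so an analyst who read the whole protocol might orient the test correctly. The analysis paragraph does not carry a non-inferiority test forward at all.

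The bound reading does have some support: when the margin is widened to 10 points, FNB stays at 98% and the second figure moves to 88%, as a bound would and an expected FNA rate would not. That makes it plausible, not established.

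Two limits on the figures also stand. The 81% needs FNB to be truly 10 points worse, a scenario that the plan does not pose. The 5% under reading A at 98% against 93% is no malfunction, because that pair is then the null boundary and rejection near alpha is expected. With equal true rates, direction makes no difference.

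What survives is that neither reading states a permitted FNB shortfall. The symmetric wording in 4.1 is a prediction, not a test specification, and is not an error in itself.

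**Conclusion.** The point holds as a conflict between 6.8.1 and 6.8.2, not as proof of a reversed test. The 5 or 10 points are FNB's lead over FNA; the stated purpose needs a limit in the opposite direction, and the plan has none. The 81% (or 68%) pass rate for a needle 10 points worse applies only if 93% is the bound. Whichever reading was meant, a 5-point test in the direction of 6.8.2 does not have 80% power with 32 patients. It has about 61% or 41% at the plan's own rates, and about 26% or 7% if both needles reach 98% (alpha 0.05 or 0.025).

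These figures rest on 1:1 allocation, the score test and independent specimens. Two specimens from one patient are unlikely to be independent, and correlation would change the percentages, but not which needle a margin protects. Because the sample size depends on this sentence, it should be corrected and not left to the analyst.

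**What to change.** In 6.8.1:

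- State H0: p(FNB) − p(FNA) ≤ −margin against H1: p(FNB) − p(FNA) > −margin.
- Name the margin (5 points if that is what was meant) and the one-sided alpha.
- Give the anticipated success rate of each needle separately from the margin.
- Conclude non-inferiority only if the one-sided lower confidence limit for FNB minus FNA is above −margin.
- Restate the power of 32 patients in this direction, with the assumption about correlation between a patient's two specimens.

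Changing 4.1 from similarity to non-inferiority would make the protocol uniform, but is optional.

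The rewrite costs a few sentences and adds no procedures. It does not repair the sample size. By the formula in Step 1, 80% power with a 5-point margin needs 53 to 67 specimens per needle at 98% against 93%, or 97 to 124 with both at 98%. At two independent specimens per patient and two needles, these are also the total numbers of patients. If 32 patients are kept, the plan should report the lower power openly.

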6.2 Study Population

6.2.1 Approximate Number of Subjects

Approximately 32 subjects will participate in this study.

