The left lobe is described as liver parenchyma identified a few centimeters below the gastroesophageal junction with the echoendoscope torqued clockwise. The right lobe is considered the large area of liver tissue can be seen through the duodenal bulb, near the gallbladder [37]. The stylet is removed, heparin flushed through the needle lumen, and the suction device set and attached to the needle hub. The prepared needle is then inserted into the echoendoscope. A transgastric approach will be used to obtain samples from the left lobe of the liver; a transduodenal approach, with the linear echoendoscope positioned in the duodenal bulb, will be used to obtain samples from the large amount of liver parenchyma seen in that location. Once adequate liver parenchymal penetration will be achieved with the needle (~2-6 cm), full suction will be applied with a 20-mL vacuum syringe. One pass consists of a total of 7 to 10 to-and-fro needle motions with the fanning technique applied under direct and continuous endosonographic visualization of the tip of the needle.

The needle will then be removed from the echoendoscope. The specimen will be pushed from the needle with the stylet directly into a microseive, and blood washed from the specimen with a gentle saline rinse. The endosonographer looks for multiple pieces of light brown tissue approximately 5 to 15 mm in length. The tissue cores are then “floated” off the microseive into formalin solution. Heparin is flushed through the needle lumen prior to the next pass. The biopsy process is then repeated on the opposite liver lobe. A pass per liver lobe will be performed in each patient; using the standard 19-g EUS-FNA needle or the 19-g EUS FNB

Date Last Modified: 10/2/2017

IRB # 2017-0391

CONFIDENTIAL AND PROPRIETARY

needle. All patients are closely observed in the recovery area for 1 hour after the procedure, as per our standard policy. Patients will be followed-up with by a phone call the next day and at 1 week after the procedure, as per standard of care.

Sample Processing

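### The 80% power claimed for 32 patients at a 5-point margin does not follow from the plan's inputs; at one-sided alpha 0.05 (assumed) exact score-test power is about 26% or 61%

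*Combined protocol and SAP*

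**What the plan says.** Section 6.8.1 assumes that the FNB needle succeeds (at least 5 portal triads) in 98% of cases, with a 5% margin over FNA written as 98% against 93%. It states that "the study needs to evaluate 32 patients to achieve 80% power for a 1-sided non-inferiority test", and adds: "This also assumes each patient provides 2 specimens". A second scenario follows: "If the margin is increased to 10% (98% vs. 88%), then the study needs to evaluate 18 patients to achieve 80% power".

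Other sections fix the design. Section 6.2.1 gives the study total: "Approximately 32 subjects will participate in this study". Section 6.5 gives each patient one pass per lobe with one needle or the other: "A pass per liver lobe will be performed in each patient; using the standard 19-g EUS-FNA needle or the 19-g EUS FNB" needle. Section 6.8.2 sets the aim as learning whether FNB "provides liver cores equal or superior to 19-g FNA needle for histologic interpretation", and supports the number only with "It is felt that 32 cases collected prospectively should be adequate".

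The only significance level, "A P-value of <0.05 will be considered statistically significant", follows the sentence on Mann-Whitney-Wilcoxon comparisons. No alpha, test statistic, allocation ratio or within-patient correlation is given for the non-inferiority comparison.

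**The concern.** Thirty-two specimens per needle is a small sample for excluding a 5-point difference between proportions near 98%, so a power of 80% looks too high. The wording also does not separate the non-inferiority margin from the assumed true difference: 93% could be the bound or the true FNA rate.

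The calculation is the only quantitative support for the sample size, and the hypothesis in section 4.1 is that the needles perform similarly. If power is overstated, a wide and inconclusive interval may be read as similarity, or a failure to show non-inferiority as a real deficit.

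**Working it through.** **Inputs.** From 6.8.1: FNB 98%, margin 5 points, two specimens per patient, one-sided test, 80% power. From 6.2.1: 32 patients in total. Assumed: 1:1 allocation, independent specimens, and one-sided alpha 0.05 (0.025 and 0.10 also run). Sixteen patients × 2 specimens = 32 specimens per needle, so specimens per needle equal total patients. Both readings of the FNA rate were run: truly 98% (98/98), and truly 93% with a further 5-point margin (98/93).

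**Trying to reproduce 32.** The normal-approximation sample size per needle is

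n = (z₁₋α + z₀.₈₀)² [p_T(1−p_T) + p_C(1−p_C)] / (p_T − p_C + m)², with T = FNB, C = FNA and (1.645 + 0.842)² = 6.183.

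- 98/98, m = 0.05: 6.183 × 0.0392 / 0.0025 = 96.9, so 97
- 98/93, m = 0.05: 6.183 × 0.0847 / 0.0100 = 52.4, so 53
- 98/98, m = 0.10: 6.183 × 0.0392 / 0.0100 = 24.2, so 25
- 98/88, m = 0.10: 6.183 × 0.1252 / 0.0400 = 19.4, so 20

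Neither 5-point result is near 32. By exact enumeration of the score test, 80% power needs 56 patients (98/93, 5 points) and 23 (98/88, 10 points).

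**Are 32 and 18 consistent with each other?** In this formula the ratio of the 5-point to the 10-point sample size does not depend on alpha, power or allocation. It is 96.9/24.2 = 4.0 if both needles are 98%, or 52.4/19.4 = 2.7 on the other reading. The plan's ratio is 32/18 = 1.8.

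**Power with 32 specimens per needle.** Normal approximation: Φ[(p_T − p_C + m)/SE − z₁₋α].

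- 98/98: SE = √(0.0392/32) = 0.0350; 0.05/0.0350 − 1.645 = −0.216; power 41%
- 98/93: SE = √(0.0847/32) = 0.0514; 0.10/0.0514 − 1.645 = 0.299; power 62%

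Exact power sums the binomial probabilities of every outcome that rejects, for the score test (variance at the restricted maximum likelihood estimate, Farrington-Manning) and for the unpooled Wald test:

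| One-sided alpha | Truth | Normal approx. | Exact score | Exact Wald |
|---|---|---|---|---|
| 0.025 | 98/98 | 30% | 7% | 53% |
| 0.025 | 98/93 | 49% | 41% | 59% |
| 0.05 | 98/98 | 41% | 26% | 53% |
| 0.05 | 98/93 | 62% | 61% | 67% |
| 0.10 | 98/98 | 56% | 57% | 57% |
| 0.10 | 98/93 | 75% | 77% | 77% |

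By normal approximation, 80% at this size needs a one-sided alpha of about 0.28 (98/98) or 0.135 (98/93). The Wald column flatters the design: at the margin (FNB 93%, FNA 98%) its true error is 10.4% against a nominal 5%; the score test's is 5.3%.

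**Best possible data.** With 32/32 on both needles the score z for a 5-point deficit is 1.298 (one-sided p = 0.097). Perfect data pass 1.645 only from 52 specimens per needle (z = 1.638 at 51, 1.654 at 52).

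**Precision.** Score-type 95% intervals for the difference are ±10.7 points at 32/32 on both needles, ±13.0 at 31/32 on both, and −10 to +18 at 31/32 (FNB) against 30/32 (FNA).

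**Two specimens from one patient.** Independence is the favourable case when each patient has one needle. At an intraclass correlation of 0.5 (assumed for illustration), 32 specimens are worth 32/1.5 = 21, and normal-approximation power falls to 32% (98/98) or 48% (98/93).

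**The case against.** The strongest alternative is that 32 was calculated per arm. With 64 specimens per needle, 98/93 and alpha 0.05, exact score power is 86%. This may be how the figure arose, and the sponsor should be asked. But section 6.2.1 makes 32 the total, the 98/98 reading still gives only 44%, and the same approach (asymptotic score) gives 13 patients on the 10-point line, not 18.

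A paired design, with both needles in each patient, could also raise power. By normal approximation at alpha 0.05 it reaches 80% with 32 pairs only if within-patient correlation is about 0.67 (98/98) or 0.46 (98/93). The plan states no such correlation, and section 6.5 describes one needle or the other.

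On the second scenario, exact Wald power at 98/88 and alpha 0.05 is 87% with 18 patients, so 18 might seem reproduced. That power is not monotonic: it exceeds 80% at 5 to 14, dips just below at 15 to 17, and stays above from 18. The same rule gives 47 patients at 5 points, so it does not rescue 32.

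It is fair to say that 26% is the least favourable result at alpha 0.05, and that it depends on an alpha, test, allocation and FNA rate that the plan does not state. The firm result is that power is below 80% in every cell of the table. It is also fair that no non-inferiority analysis is specified and that section 6.6 does not list the success criterion of at least 5 portal triads. The immediate harm is therefore an unsupported power statement rather than a test certain to be run and fail.

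Finally, 32 patients do better at the plan's own 10-point margin: exact score power at alpha 0.05 is 92.5% for 98/88, though 57% for 98/98. That does not show that 10 points is an acceptable margin.

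**Conclusion.** The concern holds and must be fixed. For 32 patients in total, the 80% figure at a 5-point margin is not supported under either reading of the FNA rate, by any of the three methods, at any of the three alphas. At one-sided alpha 0.05 with 1:1 allocation and independent specimens, exact score power is 25.8% (both needles 98%) or 61.4% (FNA 93%). Positive correlation between a patient's two specimens would lower these values. No single calculation tried gives both 32 and 18. The exact replacement value depends on inputs that the sponsor must supply; the conclusion that 80% does not follow from the stated inputs is robust across the settings tested.

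**What to change.** Keep 32 patients and withdraw the 80% claim in section 6.8.1. State as separate items:

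- the assumed true success rate for each needle;
- the non-inferiority margin and its direction (6.8.2 implies FNB not worse than FNA);
- alpha and the test;
- the allocation ratio, and confirmation that 32 is the total;
- how two specimens per patient are handled.

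Then restate power by an exact or score method beside those inputs, for example:

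> Thirty-two patients randomised 1:1 give 32 specimens per needle. For a 5-point margin, score test and one-sided alpha 0.05, with specimens treated as independent, exact power is about 26% if both needles are truly 98% and about 61% if FNA is truly 93%; within-patient correlation lowers this. With 31 or 32 of 32 successes on both needles, the score-type 95% confidence interval half-width is about 11 to 13 points before allowing for clustering.

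If the sponsor's alpha, test or allocation differ, recompute. Re-derive the 18-patient sentence by the same method (23 patients by exact score at 98 against 88) or delete it. In 6.8.1 and 6.8.2, describe the trial as estimating the difference with limited power for a 5-point margin.

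The cost is rewording two sections, with no extra patients and a less favourable stated power. If the sponsor wants to keep 80% at 5 points, the alternative is more patients: 56 by exact score at 98 against 93 and alpha 0.05 with independent specimens, and more if both needles are 98%.
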